The mirror pelvic exam (MPE) has been a proposed technique to decrease patient anxiety and improve comfort during an already uncomfortable examination. However, little research has focused on this modality to date. An early report from the 1970's described 90% of the patients felt more relaxed by utilization of the mirror and 76% revealed they would like a gynecologic problem demonstrated with a mirror [6]. A small study performed at California Polytechnic State University studied 15 females who underwent an MPE. Results were favorable revealing that 67% of the patients aged 18-26 years were more relaxed and had less discomfort whilst using the MPE. Additionally, it was found that 100% of the patients would like to have the mirror used in the future if they were to experience a gynecological problem and 92% would recommend this to a friend [7].

To date, there have been no trials regarding the utility of the MPE in a population with prolapse, incontinence or pelvic floor disorders. By studying this tool, we could understand better the utility of the MPE and discover if there is a specific patient population or situation in which this tool should be offered to ease patients' sense of vulnerability, pain, and anxiety.

Research Plan

- **Study Design**
Prospective Two-cohort Study
- **Setting for the study**
 - All new patients to Cincinnati Urogynecology Associates, TriHealth presenting to one of four outpatient clinics (Clifton, West Chester, Kenwood, Anderson) will be eligible.
 - They will then be approached by either a research coordinator, attending physician or fellow in the exam room or in the research coordinator's office prior to the start of their visit and offered enrollment.
 - If they agree to participate they will answer a brief questionnaire about demographics, personal experience with pelvic exam, the purpose of their visit and whether they would agree to have a mirror utilized during their pelvic exam that day.
 - If they agree to have a mirror used, then they will undergo the examination with the use of a mirror during the physician examination of the pelvic area, and receive information about the anatomy being shown. No other changes will be made to the exam performed.
 - If they decline a mirror then they will undergo our standard pelvic examination.
 - All enrolled patients will then be given a questionnaire at the completion of their pelvic exam.

- **Participants**

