 - Study population: All women 18 years of age to 80, who undergo pelvic exam by a physician at Cincinnati Urogynecology Associates, TriHealth will be approached for recruitment.
 - Inclusion/Exclusion criteria:
 - Inclusion
 - Adults 18 years of age to 80
 - New patients undergoing a pelvic exam performed by a physician at Cincinnati Urogynecology Associates, TriHealth
 - Exclusion
 - Existing patients
 - Unwillingness to participate in the study
 - Physical or mental impairment that would affect the subject's ability to visualize the mirror during examination or to complete questionnaires
 - Inability to understand English
 - **Sample size**
 - A sample size was calculated to be 68 patients in each arm based on the following:
 - A prior study by Seehusen D. et al, evaluated the vulnerability and discomfort level in patients who underwent a pelvic exam using stirrups or no stirrups. Because there are no prior studies that have evaluated vulnerability or discomfort using the mirror during pelvic examination, this study was used to develop a sample size [8].
 - The difference in mean VAS on level of vulnerability for two groups was selected to be 10.5 mm with SDs for 16.3 and 25.8 with/without intervention, respectively.[8]
 - Two group Satterthwaite t-test with a 0.05 two-sided significance level was used for sample size calculation.
 - The power was set at 80 %.
 - Assuming an estimated drop-out rate of 15%, the number of patient enrollment per arm was set to 80, for a total of 160 patients.
- **Data Collection**
 - Primary Outcome:

- Patient's level of vulnerability and discomfort before and after the pelvic exam.
- Secondary Outcomes:
 - Patient's sense of loss of control, anxiety and embarrassment during the pelvic exam.
 - Patient's level of understanding of pelvic anatomy and diagnosis after the pelvic exam.
 - Changes in the time of the examination as calculated by time performing the pelvic exam (will be performed using a timer in the room).
 - Differences in demographics and medical history between those that decline the MPE and those that consent to the MPE.
 - Patients' overall satisfaction of the entire visit.
 - Likelihood of physician referral to friends or family.
 - Patients willingness to have the MPE during future visits.
- General demographic data and medical data

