 - DOB, age, race, weight, height, BMI, religion, education level, past medical history, date of exam, duration of exam, chief complaint on initial visit, sexual activity level, outcome of visit (ie. Surgical intervention, medical intervention, none).
- **Intervention or experimental aspect of the study**
 - The patients will be addressed on their first visit in the exam room or in the research coordinator's office prior to the start of their visit. Each will be given a description of the study by a research coordinator, attending or fellow.
 - Once consent and enrolled, whether or not they refuse to have the mirror pelvic exam or not, they will be given a pre-examination questionnaire.
 - Of the patients who agree to have the mirror pelvic exam, they will then undergo routine pelvic examination by a physician with the usage of a mirror in the room. This mirror will be a roll-in mirror that is positioned in such a manner that provides the patient with adequate visualization of her female parts.
 - All physicians will be instructed on the terminology and descriptions to utilize with the exam to standardize the experience with the mirror.
 - The pelvic examination will be timed from the start of palpation of the external female genitalia and stopped at the time of last genital contact.
 - At the end of the visit, the patient will be given a questionnaire that characterizes her experience.
- **Statistical Analysis**
 - Descriptive statistics will be generated for demographic information such as age, race, BMI, Parity. Continuous variables such as level of vulnerability, pain, and anxiety on VAS will be analyzed using independent samples t-tests or Mann-Whitney U test for significant difference between groups. A multiple linear regression will be utilized for adjusting confounding variables. Categorical variables will be tested using the Fisher's exact or Pearson Chi-square tests.

Ethical Considerations

- **Informed consent**
 - Patients who agree to participate in the study will sign a written informed consent. They will be consented by one of the stated investigators or trained Research Nurse and they will receive a copy of the signed informed consent statements (ICS). A copy will be put in their medical file.
- **Privacy information**

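### Women choose their own cohort, but categorical outcomes are assigned only unadjusted tests, so baseline differences can appear as a mirror effect on some secondary outcomes

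*Combined protocol and SAP*

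**What the plan says.** The design is a "Prospective Two-cohort Study" (Research Plan, Study Design). Allocation is by the patient's own decision (Setting for the study): "If they agree to have a mirror used, then they will undergo the examination with the use of a mirror", and "If they decline a mirror then they will undergo our standard pelvic examination".

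The protocol expects that the cohorts may differ. It lists as a secondary outcome "Differences in demographics and medical history between those that decline the MPE and those that consent to the MPE".

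The Statistical Analysis section has three parts that bear on group comparisons:
- Continuous variables get a t-test or Mann-Whitney test. Vulnerability, pain and anxiety on a VAS are given as examples.
- Confounding is handled in one sentence: "A multiple linear regression will be utilized for adjusting confounding variables". It names no outcomes and no covariates.
- For the rest: "Categorical variables will be tested using the Fisher's exact or Pearson Chi-square tests".

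No logistic or ordinal model, stratified test, matching, weighting or propensity method appears anywhere in the document.

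The secondary outcomes include "Patients' overall satisfaction of the entire visit", "Likelihood of physician referral to friends or family", and the patient's understanding of her anatomy and diagnosis. No measurement scale is stated for any of these.

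**The concern.** The plan recognises confounding, but it ties adjustment to a model normally used for continuous outcomes. It gives categorical variables tests that cannot adjust. An analyst following the text would compare, for example, the share of satisfied women between cohorts by chi-square and read the p-value as evidence about the mirror.

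Women who accept a mirror may differ from those who decline in age, education, complaint or earlier experience of pelvic exams. If such a trait also predicts the answer, the unadjusted comparison mixes its effect with that of the mirror. The Purpose of Study section frames satisfaction and awareness as comparisons with and without the mirror, so these results will be read as effects and not only as description.

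**Working it through.** **1. The plan's own figure.** Inputs from the Sample size section: difference 10.5 mm, SDs 16.3 and 25.8, two-sided 0.05, Satterthwaite t-test, 80% power. The standard error at 68 per arm is √[(16.3² + 25.8²)/68] = √(931.33/68) = 3.70 mm, so the noncentrality is 10.5/3.70 = 2.84. Power from the noncentral t distribution is 80.3% at 68 and 79.7% at 67, so 68 reproduces. With 15% drop-out, 68/0.85 = 80 per arm, 160 in total, which also reproduces. I use 68 per cohort below. An equal split is an assumption, because women choose.

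**2. What the unadjusted tests do when the mirror has no effect.** The documents give no response rates and no imbalance, so every input here is an assumption. Let a binary pre-exam trait be present in a share c of a cohort, and let it raise the probability of a favourable answer from s0 to s1, whatever the exam. The expected share of favourable answers is

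p = c·s1 + (1 − c)·s0.

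- Mild: c = 60% (mirror) v 40% (declined), s0 = 60%, s1 = 80%. p = 0.6·0.80 + 0.4·0.60 = 72% v 0.4·0.80 + 0.6·0.60 = 68%.
- Moderate: c = 70% v 40%, s0 = 60%, s1 = 85%. p = 0.7·0.85 + 0.3·0.60 = 77.5% v 0.4·0.85 + 0.6·0.60 = 70%.
- Strong: c = 70% v 30%, s0 = 55%, s1 = 85%. p = 0.7·0.85 + 0.3·0.55 = 76% v 0.3·0.85 + 0.7·0.55 = 64%.

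The rejection rate is the sum, over all pairs (x1, x0), of Bin(x1; 68, p1)·Bin(x0; 68, p0) for those pairs with a two-sided p-value below 0.05. Chi-square is without continuity correction.

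| Scenario | Trait–cohort OR | Trait–answer OR | False difference | Chi-square | Fisher |
|---|---|---|---|---|---|
| Balanced (50% v 50%; 60% to 80%) | 1.0 | 2.7 | 0 points | 5.1% | 3.3% |
| Mild | 2.25 | 2.67 | 4 points | 8.1% | 5.7% |
| Moderate | 3.5 | 3.8 | 7.5 points | 16.8% | 12.7% |
| Strong | 5.4 | 4.6 | 12 points | 33.7% | 27.4% |

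These are exact sums. Simulation of the same scenarios scatters around them, up to 35% for chi-square and 28% for Fisher in the strong case.

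**3. What adjustment does.** I simulated 6,000 data sets for each of the mild, moderate and strong scenarios and regressed the answer on cohort and trait. The simulation standard error is √(0.05·0.95/6000) = 0.3 points.
- Logistic regression rejected in 5.1%, 5.0% and 4.9%.
- Linear regression of the 0/1 answer rejected in 5.2%, 5.1% and 5.1%.

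Both restore the nominal level, provided the trait is measured and included.

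**4. Other assumed inputs.** Take trait shares of 60% v 40%, 65% v 35% or 70% v 30%, and answer rates raised from 50% to 70%, 50% to 80% or 40% to 80%. In the eight imbalanced combinations run, the false difference was 4 to 12 points. Chi-square rejected in 7% to 32%, Fisher in 5% to 26%, and adjusted logistic regression in 4.5% to 5.6%.

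**The case against.** The strongest reply is that the regression sentence stands alone and is not restricted to VAS outcomes. A reader might infer from the separate categorical sentence that the named linear regression could not correct the bias. That does not hold: applied to a 0/1 answer with the confounder included, it brings the error rate back to about 5% (step 3). What remains is that the plan does not say the regression covers categorical outcomes, and the sentence that follows it assigns them unadjusted tests.

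Second, a reader might take satisfaction, referral and understanding to be categorical. The documents do not show this. The questionnaire is not included, the VAS list is open-ended, and each item could be a VAS or a numeric rating. If all are, the gap closes. A categorical form is plausible, because the Background reports similar items from earlier mirror studies as percentages (92% would recommend it to a friend).

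Third, it is tempting to add that the order of graded answers is thrown away. Mann-Whitney is in the plan and suits ordered scores, so order is lost only if the team classes such answers as categorical.

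Fourth, unadjusted Fisher or chi-square is right for describing how acceptors differ from decliners, which is itself a listed outcome. This stands, and the fix keeps it.

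Finally, the upper figures need a trait with odds ratios of about 5 with both cohort and answer. In the mild case chi-square rejects in 8%, and Fisher in about 6%.

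**Conclusion.** The concern holds, with limits. For any secondary outcome that turns out to be binary or ordered, the plan as written can report a baseline difference as a mirror effect. With no true effect and 68 per cohort, the false-positive rate is about 8% to 34% with chi-square and 6% to 27% with Fisher, against about 5% after adjustment. That range illustrates assumed confounding; it is not an estimate for this population. With balanced cohorts there is no inflation.

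A reader might extend the point to the main result. The documents do not support that: vulnerability and pain are named as VAS measures, which the linear regression suits, and the sample size reproduces. The change is worth making before analysis, but it concerns secondary outcomes only.

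**What to change.** State the scale of each secondary outcome, then replace the categorical sentence with wording such as:

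> Binary outcomes of the exam will be compared by logistic regression and ordered answers by proportional-odds regression, adjusted for age, education, chief complaint and prior pelvic exam experience, with odds ratio and 95% CI. Where a category is sparse, a penalised fit or fewer covariates will be used. Fisher's exact or chi-square tests will be used only to describe baseline differences between acceptors and decliners. Results will be reported as associations.

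The covariates are examples and should be few. They must be named, because the present regression sentence names none. All four are already collected, in the demographic and medical data or the pre-exam questionnaire.

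**Cost.** Wording and a few extra models; no new data and no change to the sample size. Sparse answers are the real downside. If 90% of 136 women were satisfied (assumption), 0.10·136 ≈ 14 would not be, and four covariates, some with several levels, could make the odds ratios unstable; hence the penalised or reduced model. Adjustment removes only measured confounding. It would not rescue willingness to have the mirror at future visits, which is nearly defined by the choice that formed the cohorts; report that outcome descriptively by cohort.
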